7.2.2. Dosing Schedule

If any study drug is discontinued (olaratumab or chemotherapy), the patient will be discontinued from the trial. A change of body weight $\geq 10\%$ (increase or decrease) from baseline will result in re-calculation of dose to be administered.

The following treatments will be administered in this study every 3-week (21-day) ± 3 day cycle ([Table JGDN.7.1](#) and [Table JGDN.7.2](#)).

Part A:

Cycle 1

Olaratumab as IV infusion on Day 1 and Day 8 (at 15 mg/kg)

Cycle 2 and beyond

Olaratumab as IV infusion on Day 1 and Day 8 (at 15mg/kg, or 10 mg/kg if de-escalated),

AND

Doxorubicin as IV infusion on Day 1 and Day 2 (at 37.5 mg/m²; up to 6 cycles or a cumulative dose of 450 mg/m²)

OR

Vincristine as IV on Day 1 and Day 8 (patients ≥ 10 kg: 1.5 mg/m², patients <10 kg: 0.05 mg/kg. Dose is capped at 2 mg) plus irinotecan as IV on Days 1, 2, 3, 4, 5 (at 50 mg/m²),

OR

Ifosfamide as IV on Days 1, 2, 3, 4, and 5 (at 2.8 g/m²; up to 6 cycles or a cumulative dose of 84 g/m²). Treatment beyond 84 g/m² requires consultation with the Lilly CRP/CRS.

Part B:

Cycle 1

Olaratumab as IV infusion on Day 1 and Day 8 (at 20 mg/kg)

Cycle 2 and beyond

Olaratumab as IV infusion on Day 1 and Day 8 (at 20 mg/kg),

AND

Doxorubicin as IV infusion on Day 1 and Day 2 (at 37.5 mg/m²; up to 6 cycles or a cumulative dose of 450 mg/m²)

OR

Vincristine as IV on Day 1 and Day 8 (patients ≥ 10 kg: 1.5 mg/m², patients <10 kg: 0.05 mg/kg. Dose is capped at 2 mg) plus irinotecan as IV on Days 1, 2, 3, 4, 5 (at 50 mg/m²),

OR

Ifosfamide as IV on Days 1, 2, 3, 4, and 5 (at 2.8 g/m²; up to 6 cycles or a cumulative dose of 84 g/m²). Treatment beyond 84 g/m² requires consultation with the Lilly CRP/CRS.

Part C:

All Cycles

Olaratumab as IV infusion on Day 1 and Day 8 (at 20 mg/kg),

AND

Doxorubicin as IV infusion on Day 1 and Day 2 (at 37.5 mg/m²; up to 6 cycles or a cumulative dose of 450 mg/m²)

OR

Vincristine as IV on Day 1 and Day 8 (patients \geq 10 kg: 1.5 mg/m², patients <10 kg: 0.05 mg/kg. Dose is capped at 2 mg) plus irinotecan as IV on Days 1, 2, 3, 4, and 5 (at 50 mg/m²),

OR

Ifosfamide as IV on Days 1, 2, 3, 4, and 5 (at 2.8 g/m²; up to 6 cycles or a cumulative dose of 84 g/m²). Treatment beyond 84 g/m² requires consultation with the Lilly CRP/CRS.

Table JGDN.7.1. Treatment Regimens/Dosing Schedule (Parts A and B)

Study Drug		Dose	Route	Timing

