7.2.3.1. Dose-Limiting Toxicity Determination and Maximum Tolerated Dose Definition

A DLT is defined as an adverse event (AE) during the first 21 days that is possibly related to the study drug and fulfills any one of the following criterion using the National Cancer Institute's (NCI) Common Terminology Criteria for Adverse Events (CTCAE) v 4.0:

- CTCAE Grade ≥ 3 nonhematologic toxicity. Exceptions will be made for:
 - Grade 3 febrile neutropenia without complications,
 - Grade 3 events of nausea, vomiting, diarrhea, transient electrolyte abnormalities, and constipation that can be controlled with optimal medical management within 48 hours, and
 - transient Grade 3 elevations of ALT and/or AST lasting fewer than 8 days, without evidence of other hepatic injury may not be considered a DLT if agreed by the study investigator and Lilly CRP/CRS.
- Grade 4 neutropenia that lasts longer than 2 weeks
- Grade ≥ 3 thrombocytopenia complicated by hemorrhage
- Any hematologic toxicity that causes a cycle delay of > 14 days
- Any other significant toxicity deemed by the primary investigator and Lilly clinical research personnel to be dose limiting (for example, any toxicity that is possibly related to the study medication that requires the withdrawal of the patient from the study during Cycle 1)

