7.2.3.2. Dose-Escalation Method

Part B will be initiated after the following criteria have been met:

- Acceptable safety results, which must include a minimum of 6 evaluable patients, and the PK profile from Part A monotherapy
- At least one of the 15 mg/kg combination arms has met the following DLT criteria: less than one third (that is, approximately 33.3% [minimum of 3 patients]) DLT rate. Only the combination arms in Part A that have met these criteria may be studied in Parts B and C.

In Part A, if the DLT rate is $> 1/3$ (that is, greater than 4 out of 12 patients) during Cycle 1 monotherapy, then the dose of olaratumab will be reduced to 10 mg/kg. In Part B, if the DLT rate is $> 1/3$ during Cycle 1 monotherapy, then the dose of olaratumab will be reduced to

15 mg/kg. In Part C, if the DLT rate is >1/3 during Cycle 1 combination therapy, then the dose of olaratumab will be reduced to 15 mg/kg.

If the DLT rate is >1/3 in the first cycle (Parts A and B Cycle 2, or Part C Cycle 1) of any of the chemotherapy arms, then appropriate dose de-escalation ([Table JGDN.7.3](#)) of olaratumab for that combination will occur.

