7.2.4. Dose Adjustments and Delays

In the event that a patient experiences a DLT or a DLT-equivalent (a DLT occurring in Cycle 3 or later of Parts A and B or Cycle 2 or later of Part C), treatment will be interrupted. Dosing can be resumed after resolution of the toxicity to baseline levels at the next lower dose level ([Table JGDN.7.3](#)) already deemed safe upon discussion with the Lilly CRP/CRS. For Grade 3/4 toxicities that are not dose-limiting, see Section [7.2.4.1.2](#) for hematologic toxicities and Section [7.2.4.1.3](#) for nonhematologic toxicities.

Table JGDN.7.3. Olaratumab Dose Levels and Adjustments for Olaratumab-related Toxicities

Dose at Enrollment	Dose Reduction		
	First	Second	Third
Dose level 3	20 mg/kg	15 mg/kg	10 mg/kg
Dose level 2	15 mg/kg	10 mg/kg	discontinue olaratumab
Dose level 1	10 mg/kg	discontinue olaratumab	

In the event of alteration of olaratumab therapy due to an olaratumab-related toxicity, chemotherapy need not be altered, and the planned chemotherapy schedule should be maintained. In the event that olaratumab treatment is discontinued for reason of toxicity, the patient should be discontinued from the study.

Similarly, olaratumab therapy should not be altered for chemotherapy-related toxicity, even if the chemotherapy dose is modified. In the event that chemotherapy is discontinued for reason of toxicity, the patient should be discontinued from the study.

To begin dosing at each cycle, the following criteria must be fulfilled:

- ANC $\geq 750/\text{mm}^3$
- Platelets $\geq 75,000/\text{mm}^3$
- Hemoglobin $\geq 8 \text{ g/dL}$
- Total bilirubin $\leq 1.5 \times \text{ULN}$
- AST and ALT $\leq 3.0 \times \text{ULN}$, or $\leq 5 \times \text{ULN}$ if the transaminase elevation is due to liver metastases
- Any nonhematologic toxicity that are NCI-CTCAE, v4.0 Grade <2 or equivalent severity to baseline

Treatment may be delayed for up to 14 days to allow a patient sufficient time for recovery from study drug-related toxicity.

The following information (in this section and the following subsections) pertains to dose modifications and delays for and management of AEs of concern, which may or may not be associated with olaratumab therapy, including the following:

- IRR (see Section [7.2.4.1.1](#))
- Hematologic toxicity (see Section [7.2.4.1.2](#))
- Nonhematologic toxicity (see Section [7.2.4.1.3](#))

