### 5.9.2. Adverse Events

Adverse events will be coded using the MedDRA dictionary. Severity grades will be assigned by investigators using the NCI-CTCAE Version 4.0.

The AE analysis variables have been specified in Section [5.3.1](#).

**Study drug-related AEs** are AEs that were considered to be at least possibly related to study drug by an investigator. Missing relationship is considered related to all study drugs.

The most current version of MedDRA at time of analysis will be used when reporting AEs by MedDRA terms. Unless otherwise specified, when summarized by PT, AEs will be presented in descending frequency of PT across treatment arms; when summarized by system organ class (SOC) and PT, AEs will be presented in descending frequency of PT within SOC across treatment arms. If more than one AE is recorded for a patient within any SOC or PT term, the patient will only be counted once on the most severe grade and the closest relationship to treatment.

Dose-limiting toxicities and DLT-equivalent toxicities will be listed by cohorts.

An overall summary of AEs will be provided to summarize the following categories using frequency counts and percentages by dose cohorts and combination arms:

- patients with at least one treatment-emergent adverse event (TEAE), serious adverse event (SAE), or CTCAE Grade 3 or 4 TEAE
- patients with AEs that led to death (all, up to 30 days after last dose of study drug), or discontinuation of study drug regimen

The summary will be provided for regardless of study drug causality, and repeated for events deemed by the investigator to be related to study treatment.

Treatment-emergent adverse events (TEAEs) will be summarized/listed as follows:

- treatment-emergent AE by system organ class (SOC) and PT
- study drug related TEAE
- summary of TEAEs by worst CTCAE grade
- consolidated TEAEs by consolidated category and PT
- study drug related consolidated TEAE

- summary of TEAEs by PT and descending frequency
- listing of TEAE leading to death (on treatment and within 30 days of last dose of study drug)
- listing of TEAE leading to discontinuation of olaratumab, chemotherapy, or any study drug
- listing of TEAEs leading to dose modification of any study drug, olaratumab, or chemotherapy

A patient listing of all AEs will be provided.

The following treatment-emergent SAE summaries will be provided:

- summary of treatment-emergent SAE by SOC and PT
- summary of study drug-related treatment-emergent SAE by SOC and PT

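### The DLT definition does not say which drug it covers, so Section 7.2.4 points two ways for a DLT attributed only to chemotherapy, and the combination DLT count depends on the reading

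*Protocol*

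**What the plan says.** **Definition.** Protocol 7.2.3.1: "A DLT is defined as an adverse event (AE) during the first 21 days that is possibly related to the study drug", followed by the toxicity criteria. SAP 5.3.1 uses the same attribution wording. Neither names the drug.

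**How the term is used elsewhere.** Protocol 7.2.2 counts chemotherapy as study drug: "If any study drug is discontinued (olaratumab or chemotherapy), the patient will be discontinued from the trial". Tables JGDN.7.1 and 7.2 list the chemotherapies in the study drug column. SAP 5.9.2 uses the plural: "Missing relationship is considered related to all study drugs".

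**Patient-level rule.** Protocol 7.2.4 opens with a rule for any DLT or DLT-equivalent, with no condition on cause: "treatment will be interrupted", and then "Dosing can be resumed after resolution of the toxicity to baseline levels at the next lower dose level", by reference to Table JGDN.7.3 and after discussion with the sponsor. That table lists olaratumab doses only and is captioned "Olaratumab Dose Levels and Adjustments for Olaratumab-related Toxicities". Further down, the same section says "olaratumab therapy should not be altered for chemotherapy-related toxicity, even if the chemotherapy dose is modified".

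**Arm-level rule.** Under Protocol 7.2.3.2, a DLT rate above one-third in the first combination cycle "of any of the chemotherapy arms, then appropriate dose de-escalation" of olaratumab follows for that combination. No condition on attribution is stated.

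**The concern.** DLT is one of the two components of the primary endpoint (Protocol 6.2.1). The combination DLT rate decides whether a Part A arm may be studied in Parts B and C, and whether olaratumab is lowered for that arm. If one site reads the definition as olaratumab only and another as any drug in the regimen, the same event is a DLT at one and not at the other. Even where both call it a DLT, 7.2.4 gives two instructions about the next olaratumab dose. The count then reflects how the text was read as well as what happened to the patients.

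**Working it through.** **1. Can a chemotherapy-only event meet the DLT criteria while chemotherapy continues?** Yes, in at least two foreseeable cases.
- Vincristine: Table JGDN.7.8 holds the drug for Grade 3 or 4 neurotoxicity and then resumes it at a reduced dose. Neurotoxicity is not among the exceptions in 7.2.3.1.
- Irinotecan: Table JGDN.7.11 holds the drug for Grade 3 or 4 diarrhea and then resumes it at a lower level. The exception in 7.2.3.1 covers Grade 3 diarrhea only if controlled within 48 hours.

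**2. What happens to olaratumab then?**
- *Study drug* read as olaratumab only: the event is not a DLT, the opening rule of 7.2.4 does not apply, and olaratumab is unchanged.
- *Study drug* read as any drug in the regimen: the event is a DLT. The opening paragraph interrupts treatment and describes no return at the same olaratumab dose. The later paragraph says olaratumab should stay as it is. The two do not fit together.

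**3. The plan's own cut-off.** Protocol 6.2 and 7.2.3.2 equate a rate above 1/3 with more than 4 of 12. Since 4/12 = 1/3 exactly, that means at least 5 of 12, which agrees. The same rule means at least 2 of 3 and at least 6 of 15.

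**4. How far the reading could move the arm-level decision.** Inputs: n = 3, the minimum arm size in 7.2.3.2; n = 15, the number per chemotherapy arm for Parts B and C together in 6.2. *Assumed*: a chemotherapy-only DLT probability q of 0.10, 0.20 or 0.30, since the documents give none; olaratumab adds no DLTs; patients are independent; and the rule is applied once to the whole arm.

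For n = 3: P(X ≥ 2) = 3q²(1 − q) + q³.
- q = 0.10: 0.027 + 0.001 = 0.028
- q = 0.20: 0.096 + 0.008 = 0.104
- q = 0.30: 0.189 + 0.027 = 0.216

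For n = 15: P(X ≥ 6) = 1 − Σ C(15,k) qᵏ(1 − q)¹⁵⁻ᵏ, with k from 0 to 5.

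| q | 3-patient arm above 1/3 | 15-patient arm above 1/3 |
|---|---|---|
| 0.10 | 2.8% | 0.2% |
| 0.20 | 10.4% | 6.1% |
| 0.30 | 21.6% | 27.8% |

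**5. How much naming olaratumab would remove.** If attribution were perfect, all of it, because the olaratumab rate was set to zero. In practice less. Protocol 8.1.2 calls an event possibly related unless a link is impossible, and counts possibly related as related. As an illustration, suppose half of the chemotherapy-only DLTs were still judged possibly related to olaratumab. The counted rate at q = 0.30 becomes 0.15, and the probabilities fall to 6.1% (n = 3) and 1.7% (n = 15). At q = 0.20 the counted rate is 0.10, giving 2.8% and 0.2%.

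**The case against.** The strongest reply is that 7.2.4 can be read as a general rule followed by two attribution-specific ones. Resumption is permitted, not ordered. The caption of Table JGDN.7.3 limits it to olaratumab-related toxicity, as Tables 7.4 and 7.5 are limited, and each chemotherapy has its own tables. This stands to the extent that a reader who infers that 7.2.4 both requires and forbids a lower olaratumab dose goes too far. It does not remove the inconsistency: interruption is mandatory, the opening sentence covers every DLT, and a table caption cannot settle which events are DLTs.

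Other stronger inferences are also unsupported.
- *The arm-level rule is itself an error.* The objective is a dose of olaratumab in combination, and SAP 5.13 asks about a tolerated combination. Counting every combination DLT and adjusting the investigational drug is a coherent design choice; it only has to be stated.
- *Attribution is all that separates olaratumab from chemotherapy toxicity.* Parts A and B give each patient a monotherapy cycle with its own DLT assessment. That does not isolate toxicity arising from the combination, but it is direct evidence on olaratumab.
- *Grade 3 or 4 ifosfamide neurotoxicity shows the conflict.* Where that row of Table JGDN.7.13 applies, ifosfamide is discontinued and the patient leaves the study, so no olaratumab dose remains in dispute.
- *One DLT in three failing the entry criterion for Parts B and C measures this problem.* That turns on how the less-than-one-third wording is read, and arises under any attribution rule.
- *Attribution by drug is not collected.* The case report form is not available here. Protocol 8.1.2 collects relatedness, and SAP 5.9.2 separates olaratumab from chemotherapy in some listings.

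Documented joint review by investigators and sponsor before dose escalation should also limit differences between sites, though it does not supply the missing definition.

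**Conclusion.** The point holds as a defect of definition and consistency. The drug in the DLT definition is unnamed, and 7.2.4 gives incompatible directions for a chemotherapy-only DLT when chemotherapy continues. This rests on the text alone. Because it feeds a primary-endpoint count and the one-third rules, it should be corrected.

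The numerical effect is not known. The figures of 2.8% to 21.6% (3 patients) and 0.2% to 27.8% (15 patients) rest on assumed chemotherapy DLT rates of 10% to 30% and no olaratumab contribution. The exceptions in 7.2.3.1 for uncomplicated febrile neutropenia and promptly controlled gastrointestinal events keep the true chemotherapy rate lower than it would otherwise be. The figures show what could hang on the reading; they do not estimate bias in this trial.

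**What to change.** 1. In Protocol 7.2.3.1 and SAP 5.3.1, name the drug or drugs to which a DLT must be possibly related: olaratumab, the chemotherapy, or either.
2. Reconcile the paragraphs of 7.2.4 so that a DLT attributed only to chemotherapy leads to one stated action, and say in 7.2.3.2 whether such DLTs count toward the arm-level rate. Which rule is clinically right is for the clinical team.
3. In the cohort reviews and the final DLT table, give each arm's rate twice: possibly related to any study drug, and possibly related to olaratumab. State in advance which rate drives the one-third rule. Confirm that the case report form records attribution of each DLT by drug.

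Cost: protocol and SAP wording and one more column in the DLT table. No extra patients or visits. The downside is two DLT rates to explain, which will often be close because the relatedness standard is so broad.

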7.2.4.1. Olaratumab

7.2.4.1.1. Infusion-Related Reactions

As with other monoclonal antibodies, hypersensitivity reactions may occur during or following olaratumab administration.

Patients treated with olaratumab should be closely monitored for signs and symptoms indicative of an infusion reaction by the medical staff from the start of the infusion until at least 1 hour after the end of the infusion in an area where emergency medical resuscitation equipment and other agents (for example, epinephrine, prednisolone equivalents, etc.) are available.

Olaratumab infusion reactions will be defined according to the NCI-CTCAE Version 4.0 definition of infusion-related reactions.

Symptoms occurring during or following infusion of investigational therapy may also be defined according to AE categories such as allergic reaction, anaphylaxis, or cytokine release syndrome (NCI-CTCAE Version 4.0 section “Immune system disorders”). In the setting of symptoms occurring during or following infusion of investigational therapy, investigators are encouraged to use the AE term “infusion-related reaction” and any additional terms (including those not listed here) that best describe the event.

In general, if a patient experiences a Grade 1 or 2 IRR, the infusion should stop and the patient should be treated with an antihistamine (for example, diphenhydramine hydrochloride), glucocorticoid (for example, dexamethasone), acetaminophen (or equivalent), and oxygen (as indicated), according to standard medical practices. After recovery, the infusion rate should be decreased 50% for the duration of the infusion. If subsequent infusions are then tolerated with the use of premedications as above and a 50% decrease in infusion rate, the infusion rate may be increased to a rate deemed appropriate by the investigator, as long as it does not exceed 25 mg/min.

A Grade 3 or 4 IRR will require immediate treatment, including, but not limited to, the use of epinephrine, bronchodilators, and/or glucocorticoids for symptomatic bronchospasm, IV fluids and/or pressors for hypotension, and immediate and permanent discontinuation of olaratumab with appropriate supportive care.

For a patient who has had a Grade 1 or 2 olaratumab infusion reaction in a previous cycle, patients should be premedicated with antihistamine and glucocorticoid (for example dexamethasone) intravenously 30 to 60 minutes prior to olaratumab infusion, and acetaminophen (or equivalent) for all subsequent infusions. Additional premedication may be provided at investigator discretion.

If a patient experiences an IRR to olaratumab, all attempts should be made to obtain anti-olaratumab antibody and olaratumab PK blood samples as close to the onset of the event as possible, at the resolution of the event, and 30 days (± 3 days) following the event. The procedure for sample collection and handling is described in a separate procedural manual.

7.2.4.1.2. Hematologic Toxicity

Table JGDN.7.4 summarizes the olaratumab dose modifications required in case of olaratumab-related hematologic toxicities during any cycle.

Table JGDN.7.4. General Guidelines for Olaratumab Dose Modification Due to Hematologic Toxicity Deemed Related to Olaratumab

Toxicity	Required Dose Modification
Neutropenia	
ANC Grade 1-3	No dose modification required
ANC $<500/\text{mm}^3$ (Grade ≥ 4)	No treatment administered; treatment cycle delayed
At retreatment:	
If Grade ≥ 3 neutropenic fever/infection has occurred	Withhold dose until ANC is $\geq 750/\text{mm}^3$; for the 15-mg/kg cohort (Part A), reduce dose to 10 mg/kg; for the 20-mg/kg cohort (Part B and Part C), reduce dose to 15 mg/kg.
If Grade 4 neutropenia lasting >1 week has occurred	Withhold dose until ANC is $\geq 750/\text{mm}^3$; for the 15-mg/kg cohort (Part A), reduce dose to 10 mg/kg; for the 20-mg/kg cohort (Part B and Part C), reduce dose to 15 mg/kg.
Grade 4 ANC without fever/infection lasting ≤ 1 week	Administer the next olaratumab at full dose at investigator's discretion with recommended use of prophylactic G-CSFs
Second incidence of either:	
1) Grade ≥ 3 neutropenic fever/infection	For the 15-mg/kg cohort (Part A) that have been reduced to 10-mg/kg, discontinue olaratumab; for the 20-mg/kg cohort (Part B and Part C) that have been reduced to 15-mg/kg, a second dose level reduction to 10 mg/kg
2) Grade 4 neutropenia lasting > 1 week	
Thrombocytopenia	
Platelets $<75,000/\text{mm}^3$	No treatment administered; treatment delayed until resolved to $\geq 75,000/\text{mm}^3$
Anemia	
Hemoglobin $<8 \text{ g/dL}$	No treatment administered; treatment delayed until resolved to $\geq 8 \text{ g/dL}$, transfusion with packed red blood cells allowed

Abbreviations: ANC = absolute neutrophil count; G-CSFs = granulocyte colony-stimulating factors.

7.2.4.1.3. Nonhematologic Toxicity

Specific guidelines for dose adjustments in patients who experience olaratumab IRRs may be found in Section 7.2.4.1.1.

General guidelines for dose modification for other nonhematologic toxicities related to olaratumab are shown in Table JGDN.7.5.

Table JGDN.7.5. General Guidelines for Dose Modification Due to Nonhematologic Toxicities Related to Olaratumab

Reaction Grade	Required Dose Modification
Grade 1	No dose modification is required.
Grade 2	At the investigator's discretion, the patient may continue to receive olaratumab per protocol, provided that the event does not pose a serious health risk or is easily treated.
Grade 3	For a Grade 3 toxicity not adequately controlled with appropriate supportive care, the dose must be withheld until toxicity is \leq Grade 1 or has returned to pretreatment baseline; then treatment may resume at a reduced dose of 10 mg/kg for the 15-mg/kg cohort (Part A) and reduced dose of 15 mg/kg for the 20-mg/kg cohort (Part B and Part C). If toxicity recurs after therapy resumes, then treatment should be discontinued for the 15-mg/kg cohort (Part A) or the dose reduced to 10 mg/kg for the 20-mg/kg cohort (Part B and Part C).
Grade 4	The dose must be withheld until dose toxicity is \leq Grade 1 or has returned to baseline. Permanent discontinuation should be considered for any patient experiencing Grade 4 non-hematologic toxicity assessed as related to olaratumab. However, if resumption of dosing is deemed appropriate by the investigator, treatment may resume only after consultation with the Lilly study physician, with the dose reduced to 10 mg/kg for the 15-mg/kg cohort (Part A); dose reduced to 15 mg/kg for the 20-mg/kg cohort (Part B and Part C). If Grade 4 toxicity recurs after therapy resumes, treatment with olaratumab will be discontinued.

